10.7.6 Efficacy Analyses

All efficacy variables involving responder rates or proportions will be analyzed using a Cochran-Mantel-Haenszel (CMH) test with pooled investigator site as a stratification (adjustment) variable. Summary statistics will include the pairwise risk difference with placebo along with the asymptotic 95% confidence interval (CI). The adjusted relative risk (adjusted for pooled investigator site) will be based on the ratio of responder rates for placebo versus tenapanor 50 mg BID. The 95% CI versus placebo will also be presented for the adjusted relative risk.

All continuous efficacy variables derived from the daily IWRS questions (i.e., average weekly CSBMs, SBMs, stool consistency, straining score, abdominal symptoms of pain, discomfort, bloating, fullness, and cramping), as well as the weekly IBS severity, constipation severity, and IBS QOL will be analyzed using an analysis of covariance (ANCOVA) model with terms for pooled investigator site, treatment, and baseline as the covariable. Degree of relief of IBS symptoms and treatment satisfaction will be analyzed using an analysis of variance (ANOVA) model with terms for pooled investigator site and treatment.

When the ANCOVA model is implemented, the least square means (LSmeans) will be presented for the actual values and change/percent change from baseline values for each treatment group with the 95% CI. Statistical testing will only be carried out using the change/percent change from baseline since the p-values are the same between the two analyses. The LSmean difference versus placebo will also be presented with the 95% CI. When the ANOVA model is implemented, all of the above statistics will be presented for the actual values.

A sequential testing procedure will be utilized to control the experiment wise Type I error rate for the primary efficacy variable. Because of the desire to also pre-specify key secondary efficacy variables, the sequential testing procedure will not inflate the overall 5% level. The primary efficacy variable will be tested at the 5% level of significance. If this test is significant, the first key secondary efficacy variable listed in [Table 10-1](#) will be tested at the 5% level. If this test is significant, then the next variable is tested at the 5% level. This procedure continues until one of the tests in the list results in a p-value >5%. Variables up to this point in the list will be declared statistically significant. Interpretation of p-values for the secondary efficacy variables will be descriptive.

In addition to the summaries of the efficacy variables described, figures will be provided depicting the actual means or the change/percent change from baseline for each treatment group at each assessment time. A secondary analysis will also include graphs depicting the cumulative distribution of the percentage reduction of abdominal pain.

10.7.7 Safety Analyses

Safety assessments will be based on the incidence, severity, and type of adverse events, and clinically significant changes in the subject's clinical laboratory tests, vital signs, ECGs and physical examinations.

Adverse events will be coded using the MedDRA adverse event coding system for purposes of summarization. All adverse events reported will be listed in the data listings. Treatment emergent adverse events (TEAEs) will be tabulated, where treatment emergent is defined as any adverse event which occurs after administration of the first dose of study drug and up through the final visit (up to planned Day 183), any event that is considered drug-related regardless of the start date of the event, or any event that is present at baseline but worsens in severity or is subsequently considered drug-related by the investigator. TEAEs will also be tabulated by whether events are considered related to treatment (possibly or probably drug-related, or unknown in relationship) and by severity. Serious adverse events and TEAEs resulting in study discontinuation will be tabulated.

Actual values and change from baseline values for clinical laboratory tests will be summarized for each visit collected during the study. The frequency of clinically significant abnormal laboratory test values will be tabulated by treatment group. Shift tables will be derived for changes in laboratory tests from screening to Visit 4, 6, and 9.

Vital signs will be summarized descriptively for actual values and change from baseline values by treatment group and visit. Vital signs are collected at all study visits during the screening period and 26-week treatment period. Baseline for the vital signs will be the average of results obtained during the screening period.

Electrocardiogram results will be summarized descriptively for actual values and change from screening values by treatment group and visit (Screening (Visit 1/Day -14), Week 12 (Visit 6/Day 85), and Week 26 (Visit 9/Day 183)). The overall interpretation will be summarized with number of subjects and percentages for the normal and abnormal ECG result categories.

All vital signs and electrocardiogram results will be listed. Abnormal or clinically significant results will be flagged.

Physical examinations are collected at Screening (Visit 1/Day -14) and Week 26 (Visit 9/Day 183). The number and percentage of subjects in each category will be presented for each visit by treatment group.

All physical examination results will be listed. Abnormal physical exam results will be flagged.

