8.3.1.3 Electrocardiogram

A 12-lead electrocardiogram will be obtained during Visits 1, 6 and 9 (and at any early termination visit).

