### **3.8.2 Clinical Laboratory Tests**

The list of clinical laboratory tests collected for this study are presented in Appendix C of the protocol. Serum chemistry, hematology, and urinalysis results will be summarized with descriptive statistics at Screening (Visit 1/Day -14), Week 4 (Visit 4/Day 29), Week 12 (Visit 6/Day 85), and Week 26 (Visit 9/Day 183) by treatment group. For continuous tests, actual values and change from screening will be summarized. For categorical tests, the number and percentage of subjects in each category will be presented for each visit. Serum chemistry tests included in these summaries will be albumin, alkaline phosphatase, ALT, AST, bicarb/CO2, total bilirubin, direct bilirubin, indirect bilirubin, calcium, chloride, total cholesterol, creatinine, glucose, inorganic phosphorous, LDH, potassium, total protein, sodium, triglycerides, BUN/urea, and uric acid. Hematology tests included in these summaries will be WBC, RBC, MCV, MCH, MCHC, hemoglobin, hematocrit, and platelet count. Differentials consisting of bands, monophils, neutrophils, eosinophils, lymphocytes, and basophils will be included in the listings only. Urinalysis tests included in these summaries will be appearance, specific gravity, and pH. Protein, glucose, ketones, blood, nitrite, and microscopic results will be presented in listings only.

The frequency of clinically significant abnormal laboratory test values will be tabulated by treatment group.

Shift tables classifying normal range results (low out of normal range, normal, or high out of normal range) between Screening and Week 4 (Visit 4/Day 29), Week 12 (Visit 6/Day 85), and Week 26 (Visit 9/Day 183) values will be tabulated by treatment group. Missing results for each pairwise summary will be tabulated.

Data listings of clinical laboratory tests will include flags for abnormal results.

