### **3.8.4 Physical Examination**

Physical examinations (general appearance, HEENT, respiratory, cardiovascular, abdomen, skin, lymph nodes, musculoskeletal, extremities, and neurological) are collected at Screening (Visit 1/Day -14), and Week 26 (Visit 9/Day 183). The number and percentage of subjects in each category will be presented for each visit by treatment group.

All physical examination results will be listed. Abnormal physical exam results will be flagged.

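### The ECG-interpretation and physical-exam tables show net prevalence only and cannot count subjects who became abnormal on treatment

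*Protocol*

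**What the plan says.** Protocol 10.7.7 opens by basing the safety assessment on adverse events and on "clinically significant changes in the subject's clinical laboratory tests, vital signs, ECGs and physical examinations". SAP 3.8 opens in the same way. The planned summaries then differ by type of measurement.

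- **ECG, numeric.** "Electrocardiogram results will be summarized descriptively for actual values and change from screening values by treatment group and visit". SAP 3.8.3 names the measurements: heart rate, PR, QRS, QT, QTcB and QTcF.
- **ECG, overall reading.** "The overall interpretation will be summarized with number of subjects and percentages for the normal and abnormal ECG result categories". SAP 3.8.3 repeats this. The sentence names neither visit nor arm; the natural reading is that it inherits both from the sentence before it.
- **Physical examination.** "The number and percentage of subjects in each category will be presented for each visit by treatment group". This is SAP 3.8.4, matching Protocol 10.7.7. The SAP lists ten body systems.
- **Laboratory tests.** Protocol 10.7.7: "Shift tables will be derived for changes in laboratory tests from screening to Visit 4, 6, and 9". SAP 3.8.2 gives the layout: "Shift tables classifying normal range results (low out of normal range, normal, or high out of normal range) between Screening and Week 4", continuing to Weeks 12 and 26, with missing results counted for each pairing.

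Neither document plans a cross-classification against screening, or a count of subjects going from normal to abnormal, for the ECG reading or the physical examination.

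**The concern.** The section says it looks for changes, yet for these two results the arm-level summary contains no within-subject change. A percentage abnormal at a visit adds together findings that were there at screening and persisted, and findings that are new. Findings that resolved drop out of it. The quantity a safety reader wants is how many subjects who entered normal became abnormal in each arm, and it cannot be recovered from those margins. Safety and tolerability are the stated secondary objective, and these summaries are part of how it is reported.

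**Working it through.** **1. Which measures get a within-subject comparison.** Laboratory tests have change from screening and shift tables. Vital signs have change from baseline. Numeric ECG values have change from screening. The overall ECG reading and the physical examination have counts per category only. The SAP text does not extend the laboratory shift layout to them.

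**2. Whether the pairing is possible.** ECGs are taken at Visits 1, 6 and 9 or early termination (Protocol 8.3.1.3). Physical examinations are done at Visits 1 and 9 or early termination (Protocol 8.3.1.2). Each on-treatment result therefore has a screening result to pair with. Subjects abnormal at entry can be in the table: exclusion 7 (Protocol 5.3) concerns significant disease that may interfere with completing the trial, so an abnormal reading alone does not exclude.

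**3. Offsetting, with hypothetical counts.** Let 60 of 300 subjects be abnormal at screening in each arm. On tenapanor 30 resolve and 30 of the other 240 become abnormal; on placebo 6 resolve and 6 of 240 become abnormal.

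- Week 26 prevalence: tenapanor (60 − 30 + 30)/300 = 20%; placebo (60 − 6 + 6)/300 = 20%.
- Newly abnormal among those normal at screening: 30/240 = 12.5% v 6/240 = 2.5%.

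The planned table shows no change over time and no difference between arms.

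**4. Dilution.** The plan gives no ECG or exam abnormality rate, so there is no figure of its own to reproduce. Inputs:

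- *n* = 300 per arm (Protocol 10.1, SAP 3.1).
- Assumed: new-abnormality rates i₁ = 4% (tenapanor) and i₀ = 1% (placebo) among subjects normal at screening.
- Assumed: all screening abnormalities persist, and no dropout.
- Varied: share abnormal at screening, b = 0% to 30%.

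Prevalence in an arm is p = b + (1 − b)i, so the difference in prevalence is (1 − b)(i₁ − i₀). Its standard error is √{[p₁(1 − p₁) + p₀(1 − p₀)]/300}. For new findings the difference is i₁ − i₀, with standard error √{[i₁(1 − i₁) + i₀(1 − i₀)]/[300(1 − b)]}.

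At b = 20%:

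- Prevalence: p₀ = 0.20 + 0.80 × 0.01 = 0.208 and p₁ = 0.20 + 0.80 × 0.04 = 0.232. The difference is 0.024, with SE √{[0.232 × 0.768 + 0.208 × 0.792]/300} = 0.0338.
- New findings: the difference is 0.030, with SE √{[0.04 × 0.96 + 0.01 × 0.99]/240} = 0.0142.
- Difference divided by SE: 0.71 for prevalence and 2.11 for new findings.

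| Abnormal at screening | Prevalence, placebo v tenapanor | Difference (SE), points | Normal at screening per arm | New-finding difference (SE), points |
|---|---|---|---|---|
| 0% | 1.0% v 4.0% | 3.0 (1.27) | 300 | 3.0 (1.27) |
| 10% | 10.9% v 13.6% | 2.7 (2.67) | 270 | 3.0 (1.34) |
| 20% | 20.8% v 23.2% | 2.4 (3.38) | 240 | 3.0 (1.42) |
| 30% | 30.7% v 32.8% | 2.1 (3.80) | 210 | 3.0 (1.52) |

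**5. Incomplete persistence.** If a share r of screening abnormalities persists, p = br + (1 − b)i. With the same r in both arms the br term cancels and the differences above are unchanged. With different r the difference is (1 − b)(i₁ − i₀) + b(r₁ − r₀), and the second term can cancel the first. Step 3 is such a case: 0.8 × (0.125 − 0.025) + 0.2 × (0.5 − 0.9) = 0.08 − 0.08 = 0.

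**The case against.** The best defence is that the plan covers what matters by other routes. Protocol 9.6 requires any clinically relevant deterioration in a clinical finding to be recorded as an adverse event. The treatment-emergent definition in SAP 3.8.1 depends on onset or worsening after first dose, so those tables are incidence tables by arm. ECG intervals are analysed as change from screening. All ECG and exam results are listed by subject, with abnormal ones flagged. Screening is one of the assessment points in the ECG and exam summaries, so net change in prevalence can be read off. The missing table could also be produced later from data already collected. All of this stands, and it limits the point to the arm-level summary; data capture is not in question.

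Three parts carry less weight. The adverse-event rule rests on the investigator's judgement of relevance, and it names laboratory tests too, yet the plan still gives those shift tables. Listings allow subject-level review but do not compare arms. SAP 4 puts table layouts in a separate programming document that is not available here, so the final table set cannot be confirmed; but the SAP specifies laboratory shifts in words and is silent here, so nothing in it requires them.

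A reader might infer more: that new abnormalities are hidden altogether, that the comparison between arms is biased, or that the trial loses a definite amount of power. The documents do not support any of these. Randomization leaves the prevalence difference unbiased for what it measures, though diluted as a measure of new findings. No test of these safety tables is planned, so power is not a property of this plan. The rates in the working are assumptions, and the dilution disappears as the screening rate approaches 0%, where some individual body systems may well lie.

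**Conclusion.** The point holds as a limited reporting gap. The categorical ECG and physical-exam summaries give net prevalence, are not linked to screening, and cannot count subjects who became abnormal on treatment. Reading change by comparing the screening and Week 26 percentages is not a full substitute: new and resolved findings offset each other, and after dropout the two percentages rest on different subjects.

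The size is illustrative. Under the assumed 4% v 1%, up to 0.9 of the 3.0 points is lost at 30% abnormal at screening and nothing at 0%; pre-existing findings add noise in between. The standard errors describe that noise and are not error rates of any planned analysis. No efficacy conclusion depends on this, and numeric ECG and laboratory summaries are unaffected.

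**What to change.** Keep the visit counts. In SAP 3.8.3 and 3.8.4 add, by arm and in the SAP 3.8.2 layout with missing results counted:

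- a shift table for the overall ECG interpretation, Screening to Week 12 and Screening to Week 26/early termination;
- a shift table for each physical-exam body system, Screening to Week 26/early termination;
- the number and percentage newly abnormal among subjects normal at screening. For the ECG, count any post-dose assessment; the exam has only one, so its count comes from the same visit as its shift table.

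State in SAP 3.8.3 that the overall ECG interpretation is tabulated by visit and arm. The cost is a few SAP sentences and two extra table programs, with no new data or procedures. SAP 4 has the programming specifications finalized before database lock, so the additions belong there at the same time.

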11. ADMINISTRATIVE REQUIREMENTS

11.1. Good Clinical Practice

The study will be conducted in accordance with the current GCP/ICH Guidelines and relevant regulatory requirement(s). Compliance with this standard provides public assurance that the rights, safety and well-being of trial subjects are protected; consistent with the principles that have their origin in the Declaration of Helsinki and that the clinical trial data are credible. The Investigator will be thoroughly familiar with the appropriate use of the study drug as described in the protocol and Investigator's Brochure. Essential clinical documents will be maintained to demonstrate the validity of the study and the integrity of the data collected. A Trial Master File will be established at the beginning of the study, maintained for the duration of the trial and retained according to appropriate regulations.

11.2. Ethical Considerations

The study will be conducted in accordance with ethical principles that have their origin in the Declaration of Helsinki. The IRB/IEC will review all appropriate study documentation in order to safeguard the rights, safety and well-being of the subjects. The study will only be conducted at sites where IRB/IEC approval has been obtained. The protocol, Investigator Brochure, informed consent, advertisements (if applicable), written information given to the subjects (including subject information material), safety updates, annual progress reports, and any revisions to these documents will be provided to the IRB/IEC by the Investigator.

11.3. Subject Informed Consent and Information

Prior to entry in the trial, the Investigator must explain to potential subjects or their legally acceptable representative, the trial and the implications of participation. Subjects will be told that their participation is voluntary and they may withdraw consent to participate at any time. Subjects will be told that competent authorities and authorized Ardelyx personnel, its business partners or its CRO designee may access their records without violating the confidentiality of the subject, to the extent permitted by the applicable law(s) and/or regulations. By signing the Informed Consent Form (ICF) the subject or legally acceptable representative is authorizing such access through an authorization meeting the requirements of the Health Insurance Portability and Accountability Act of 1996. Each subject (or their legally authorized representative) that wants to participate in the study must sign and date the ICF (and other locally required documents) after the nature of the study has been fully explained prior to performing any study-related activities. The subject (or their legally acceptable representative) will be given sufficient time to read the ICF and to ask additional questions. After having obtained the consent, a copy of the informed consent document must be given to the subject. In case the subject is unable to read, an impartial witness must attest the informed consent. Subjects who are unable to comprehend the information provided can only be enrolled after consent by a legally acceptable representative.

The consent form that is used must be approved by both the reviewing IRB and by Ardelyx or its CRO designee.

All reports and communications relating to the study will identify subjects by initials and assigned number only. A “Subject Screening Log” that reports on all subjects that were seen to determine eligibility for inclusion in the trial will also be completed by the Investigator.

11.4. Subject Confidentiality

The collection and processing of data from subjects enrolled in this trial will be limited to those data that are necessary to investigate the safety, quality and utility of the investigational product(s) used in this trial. These data will be processed with adequate precautions to ensure confidentiality.

In order to maintain subject/subject privacy, all CRFs, study drug accountability records, study reports and communications will identify the subject by initials and the assigned subject number. The Investigator will grant monitor(s) and auditor(s) from Ardelyx, its designee(s) and regulatory authority(ies) access to the subject’s original medical records for verification of data gathered on the CRFs and to audit the data collection process. The subject’s confidentiality will be maintained and will not be made publicly available except to the extent permitted by the applicable laws and regulations.

11.5. Protocol Compliance

The Investigator will conduct the trial in compliance with the protocol provided by Ardelyx, and given approval by the IRB/IEC and the appropriate regulatory authority(ies). Modifications to the protocol should not be made without agreement of both the Investigator and Ardelyx. Changes to the protocol will require written IRB/IEC approval prior to implementation, except when the modification is needed to eliminate an immediate hazard(s) to subjects. The IRB/IEC may provide, if applicable regulatory authority(ies) permit, expedited review and approval for minor change(s) in ongoing trials that have the approval of the IRB/IEC. Ardelyx will submit all protocol modifications to the regulatory authority(ies) in accordance with the governing regulations.

When immediate deviation from the protocol is required to eliminate an immediate hazard(s) to subjects, the Investigator will contact Ardelyx, if circumstances permit, to discuss the planned course of action.

11.6. Study Monitoring and On-site Audits

Monitoring and auditing procedures developed by Ardelyx or its CRO designee will be followed, in order to comply with GCP guidelines. Routine monitoring visits will be made to assure compliance with the study protocol, to review and compare the subject’s eCRF with source documents, to ensure adequate records of clinical supplies are maintained and to assess the continued suitability of the investigational site. The Investigator agrees to allow the site monitors, and other authorized personnel or designees, access to the subject’s medical records, regulatory binder, study binder, and source documents as needed to assure the conduct of the study was within compliance.

Upon completion of the study the site monitor will make a final assessment of the

conduct of the study and inventory all clinical supplies to be returned to Ardelyx. All unused study drug is to be returned to Ardelyx or designee.

Regulatory authorities, the IEC/IRB, and/or Ardelyx's clinical quality assurance group, its CRO designee or business partners may request access to all source documents, CRFs, and other study documentation for on-site audit or inspection. Direct access to these documents must be guaranteed by the Investigator, who must provide support at all times for these activities.

11.7. Case Report Form Completion

An Electronic Data Capture (EDC) system will be used for this study. Electronic case report forms (eCRFs) will be accessed for each subject.

eCRFs will be completed for each screened and randomized study subject. It is the Investigator's responsibility to ensure the accuracy, completeness, and timeliness of the data reported in the subject's eCRF. Source documentation supporting the eCRF data should indicate the subject's participation in the trial and should document the dates and details of study procedures, adverse events and subject status.

The Investigator, or designated representative, should complete the eCRF pages as soon as possible after information is collected, preferably on the same day that a study subject is seen for an examination, treatment, or any other study procedure. Any outstanding entries must be completed immediately after the final examination. An explanation should be given for all missing data.

Prior to submission within the EDC system, eCRFs must be reviewed for completeness and accuracy, and electronically signed and dated by the Investigator where indicated.

